6.1.2 Secondary Endpoints

The time points for the efficacy assessments are defined below. Since the baseline measures are by definition those taken prior to the start of deferiprone therapy, “baseline” is defined differently for the two groups, as follows:

- **Group 1:** For patients who received deferiprone in LA38-0411, the baseline visit of that study will be treated as the baseline visit of LA38-EXT as well. Thus, Week 0 of the extension study will be Year 1 (i.e., the completion of one year of deferiprone treatment), Week 52 will be Year 2, and Week 104 will be Year 3 of deferiprone treatment.
- **Group 2:** For patients who received deferoxamine in LA38-0411, the start of the extension study (Week 0) will be treated as the baseline visit. For this group, therefore, Week 52 will be Year 1, and Week 104 will be Year 2 of deferiprone treatment.

Efficacy endpoints for deferiprone therapy are provided below. For Group 1, the change from baseline to Year 1 is derived from study LA38-0411. For Group 2, there is no Year 3 of deferiprone treatment.

- The change from baseline to Year 1 (both groups; Group 1 data are from LA38-0411), from baseline to Year 2 (both groups), and from baseline to Year 3 (Group 1 only) in liver iron concentration (LIC), as measured by magnetic resonance imaging (MRI)
- The change from baseline to Year 1 (both groups; Group 1 data are from LA38-0411), from baseline to Year 2 (both groups), and from baseline to Year 3 (Group 1 only) in cardiac MRI T2*
- The change from baseline to Year 1 (both groups; Group 1 data are from LA38-0411 data), from baseline to Year 2 (both groups), and from baseline to Year 3 (Group 1 only) in serum ferritin
- Responder analysis, defined as the percentage of patients who show a $\geq 20\%$ decline from baseline in LIC or serum ferritin or a $\geq 20\%$ increase from baseline in cardiac MRI T2* at Year 1 (both groups; Group 1 data are from LA38-0411), at Year 2 (both groups), and at Year 3 (Group 1 only)

In addition to the above analyses, the change from baseline to end of LA38-041 for deferoxamine and the change from baseline to end of LA38-EXT for deferiprone in Group 2 will be compared. The purpose of this analysis is to assess if deferiprone could maintain or even further improve LIC and MRI T2* after the patients were switched therapy.

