3 STUDY DESIGN

LA38-EXT is a 2-year prospective, multi-center, single-arm, open-label extension of LA38-0411. All patients who have completed LA38-0411 have been offered the opportunity to continue in this extension study, with the final visit of LA38-0411 being Visit 1 of LA38-EXT. Patients who had been treated with deferiprone during LA38-0411 continued to receive deferiprone for up to 2 years (Group 1), while those who had been treated with deferoxamine were switched to deferiprone for treatment up to 2 years (Group 2) in LA38-EXT. The dosage of deferiprone was 25–33 mg/kg three times a day (t.i.d.).

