6.3.3 Analysis of Efficacy

Changes in LIC, in cardiac MRI T2*, and in serum ferritin from baseline to Year 1 (both groups; Group 1 data are from LA38-0411), from baseline to Year 2 (both groups), and from

baseline to Year 3 (Group 1 only) will be summarized with descriptive statistics and will be tested against no change using a one-sample t-test. The changes in these 3 efficacy measures from the start of deferiprone therapy to the last visit of LA38-EXT in all patients, irrespective of whether deferiprone therapy was initiated in LA38-0411 or in LA38-EXT, will also be tested using a one-sample t-test. In addition, the percentages of responders will be tabulated for Year 1 (both groups; Group 1 data are from LA38-0411), for Year 2 (both groups), and for Year 3 (Group 1 only) of deferiprone therapy. The change from baseline to end of LA38-041 for deferoxamine and the change from baseline to end of LA38-EXT for deferiprone in Group 2 will be compared.

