	Visit	N Mean \pm SD (Min, Max)	N Mean \pm SD (Min, Max)	P-value (T-test)
LIC (mg/g dw)	Baseline	XXX xx.x \pm xx.x (xx.x, xx.x)	XXX xx.x \pm xx.x (xx.x, xx.x)	0xxxx
	Month 6	XXX xx.x \pm xx.x (xx.x, xx.x)	XXX xx.x \pm xx.x (xx.x, xx.x)	0xxxx
	Year 1	XXX xx.x \pm xx.x (xx.x, xx.x)	XXX xx.x \pm xx.x (xx.x, xx.x)	0xxxx
	Year 2	XXX xx.x \pm xx.x (xx.x, xx.x)	XXX xx.x \pm xx.x (xx.x, xx.x)	0xxxx
	Year 3	XXX xx.x \pm xx.x (xx.x, xx.x)	XXX xx.x \pm xx.x (xx.x, xx.x)	0xxxx

Data source: 16.2.10 Listing of LIC

Table 14.2.1.2 Change in LIC at each follow-up assessment

		Treatment		
		DFP+DFP	DFO+DFP	
	Visit	N Mean \pm SD (Min, Max)	N Mean \pm SD (Min, Max)	P-value (T-test)
Change in LIC (mg/g dw)	Month 6	xxx xx.x \pm xx.x (xx.x, xx.x)	xxx xx.x \pm xx.x (xx.x, xx.x)	0xxxx
	Year 1	xxx xx.x \pm xx.x (xx.x, xx.x)	xxx xx.x \pm xx.x (xx.x, xx.x)	0xxxx
	Year 2	xxx xx.x \pm xx.x (xx.x, xx.x)	xxx xx.x \pm xx.x (xx.x, xx.x)	0xxxx
	Year 3	xxx xx.x \pm xx.x (xx.x, xx.x)	xxx xx.x \pm xx.x (xx.x, xx.x)	0xxxx

Data source: 16.2.10 Listing of LIC

Table 14.2.1.3 Change in LIC for DFO+DFP group – Data from the extension study

		DFO+DFP	
	Visit	N Mean \pm SD (Min, Max)	P-value (One sample T-test)
Change in LIC (mg/g dw)	From Year 1 to Year 2	xxx xx.x \pm xx.x (xx.x, xx.x)	0xxxx
	From Year 1 to Year 3	xxx xx.x \pm xx.x (xx.x, xx.x)	0xxxx

Data source: 16.2.10 Listing of LIC

Table 14.2.1.4 Change in LIC for DFO and DFO+DFP groups

		Treatment		
		DFO*	DFO+DFP*	
	Visit	N Mean \pm SD (Min, Max)	N Mean \pm SD (Min, Max)	P-value (T-test)
Change in LIC (mg/g dw)	End of Study	xxx xx.x \pm xx.x (xx.x, xx.x)	Xxx xx.x \pm xx.x (xx.x, xx.x)	0xxxx

Data source: 16.2.10 Listing of LIC

Note: *Patients in DFO come from LA38-0411 and patients in DFO+DFP comes from LA38-EXT.

Table 14.2.1.5 Responder analysis in LIC defined as $\geq 20\%$ decline in LIC from baseline.

		Treatment				
		DFP+DFP		DFO+DFP	P-value (Fisher's exact test)	
		N	n (%)	N	n (%)	0xxxx
Year 1	xxx	xx (xx%)	xxx	xx (xx%)	0xxxx	0xxxx
Year 2	xxx	xx (xx%)	xxx	xx (xx%)	0xxxx	0xxxx
Year 3	xxx	xx (xx%)	xxx	xx (xx%)	0xxxx	0xxxx

Data source: 16.2.10 Listing of LIC

Table 14.2.1.6 Responder analysis in LIC defined as $\geq 20\%$ decline in LIC from baseline for DFO+DFP group – Data from the extension study.

		Treatment	
		DFO+DFP	
		N	n (%)
Year 1	xxx	xx (xx%)	
Year 2	xxx	xx (xx%)	

Data source: 16.2.10 Listing of LIC

Table 14.2.2.1 Cardiac MRI T2* at each assessment

		Treatment		
		DFP+DFP	DFO+DFP	

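### The Group 2 switch contrast does not answer the purpose the SAP gives it, and its table shells read as an unpaired t-test on the same patients

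*SAP*

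**What the plan says.** SAP 6.1.2 introduces the analysis as an addition to the listed efficacy endpoints. Its purpose is to learn "if deferiprone could maintain or even further improve LIC and MRI T2* after the patients were switched therapy". SAP 6.3.3 repeats the contrast: the deferoxamine change over the parent study and "the change from baseline to end of LA38-EXT for deferiprone in Group 2 will be compared". Neither section names a test, an alpha, a confidence interval or a margin.

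The only sign of the method is in SAP 17. Shells 14.2.1.4 (LIC) and 14.2.2.4 (cardiac T2*) have one end-of-study row and two columns. Each column has its own N and mean ± SD, and there is one p-value labelled as a t-test. The footnote reads "Patients in DFO come from LA38-0411 and patients in DFO+DFP comes from LA38-EXT".

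Three other statements bear on this:

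- SAP 3 defines Group 2 as the deferoxamine patients who switched to deferiprone, "with the final visit of LA38-0411 being Visit 1 of LA38-EXT". The end value of the first change is therefore the starting value of the second.
- SAP 6.1.2 sets Group 2's deferiprone baseline at Week 0 of the extension. SAP 6.3.3 says changes from baseline "will be tested against no change using a one-sample t-test".
- Shells 14.2.1.3 and 14.2.2.3 show that within-patient test for Group 2 using extension data only, and label it explicitly as one-sample.

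**The concern.** Two things do not fit.

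First, the purpose concerns what happens to iron after the switch, and the change from Week 0 answers that. The contrast asks instead whether the second change differs from the first. It can count against deferiprone when iron kept falling, and in its favour when iron kept rising. Every Group 2 patient took deferoxamine first, so even a clean difference cannot be attributed to drug rather than period.

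Second, the two columns describe the same people and share a scan. A two-sample t-test treats them as independent, so its standard error is wrong whenever the two changes are correlated.

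At stake is the conclusion drawn about switching: the table to which the SAP attaches the switch question could point a different way from the patients' own course, with a p-value that does not have its nominal size.

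**Working it through.** The plan gives no power, alpha, SD or correlation for this contrast, so there is no figure to reproduce.

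**1. Does the contrast answer the purpose?** Two illustrative patients (LIC in mg/g, values assumed):

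- 15 to 11 on deferoxamine, then 11 to 9 on deferiprone. The changes are -4 and -2. Iron fell further after the switch, yet the contrast is 2 against deferiprone.
- Up 3, then up 1. Iron is still rising, yet the contrast is 2 in favour of deferiprone.

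At group level, assume 80 patients per column, changes in SD units, zero correlation and two-sided 5%. For a difference of 0.5, power = Φ(0.5 × √(80/2) - 1.96) = Φ(1.20) = 88.5%. The one-sample statistic is the mean deferiprone change × √80.

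| Change on deferoxamine, deferiprone | Chance the contrast is significant | Deferiprone change from Week 0, mean/SE |
|---|---|---|
| -0.5, 0 (gain held) | 88.5%, against deferiprone | 0 |
| -0.5, -0.5 (further fall) | about 5% | -4.47 |
| +0.8, +0.3 (still rising) | 88.5%, for deferiprone | +2.68 |

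At zero correlation the unpaired test has the right size, so this mismatch is separate from pairing.

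**2. What does ignoring the pairing do?** Let D1 be the deferoxamine change, D2 the deferiprone change, r their within-patient correlation and s their common SD.

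- Variance of the mean difference: 2s²(1 - r)/n. The unpaired test assumes 2s²/n.
- True SE / unpaired SE = √(1 - r).
- Type I error of the unpaired test = 2 × [1 - Φ(1.96/√(1 - r))].

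| r | √(1 - r) | 1.96/√(1 - r) | Type I error |
|---|---|---|---|
| -0.5 | 1.225 | 1.600 | 10.95% |
| -0.3 | 1.140 | 1.719 | 8.6% |
| 0 | 1 | 1.960 | 5.0% |
| +0.3 | 0.837 | 2.343 | 1.9% |
| +0.5 | 0.707 | 2.772 | 0.56% |

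Simulation with 60, 80 and 100 patients gave 10.7% to 11.1% unpaired at r = -0.5 and about 0.6% at +0.5. The paired test gave 4.8% to 5.1% throughout.

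**3. Why a negative r is plausible.** Suppose the three visits have equal variance v and equal pairwise correlation ρ. Then Var(D1) = Var(D2) = 2v(1 - ρ), and Cov(D1, D2) = ρv - v - ρv + ρv = -v(1 - ρ). Hence r = -0.5 for any ρ: the shared Visit 1 scan alone produces it. Persistent differences between patients in their rate of change push r upward, possibly above zero.

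**4. If the deferoxamine column also holds patients who did not switch.** Protocol 1.2 plans 300 patients at 2:1, so 300/3 = 100 on deferoxamine. Assume 80 or 60 continue. The variance ratio is 1 - 2r(1/100)/(1/100 + 1/n2).

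- r = -0.5, n2 = 80: 0.0325/0.0225 = 1.444; SE ratio 1.202; type I error 10.3%.
- r = -0.5, n2 = 60: 0.03667/0.02667 = 1.375; SE ratio 1.173; type I error 9.5%.
- r = +0.5: 0.9% and 1.3% respectively.

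**The case against.** The strongest reply is that the SAP already holds the right analysis. The one-sample tests in 6.3.3 and shells 14.2.1.3 and 14.2.2.3 would show the 15-to-11-to-9 patient as improving, and the contrast is only an addition. That stands: a reader might infer that the switch question has no suitable analysis, and the documents do not support that. What remains is that the SAP ties the purpose to the other table and plans no confidence interval for the one that answers it.

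A reader might also take the unpaired test as the stated method. It is not. The text names no test, and SAP 17 says the final tables may differ from the shells. The inference is still the natural one, because the SAP labels its within-patient change tests as one-sample and uses the plain label for between-group comparisons.

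Nor are the displayed figures wrong. The shells show SDs, which pairing does not alter; only the standard error behind the p-value is in question, and only if r is not zero. The documents promise no error rate for this analysis.

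Non-switchers in the deferoxamine column are an ambiguity, not an established defect. SAP 3 defines Group 2 as patients who switched, and the footnote may only name the data source.

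Finally, a reader might infer that fixed order must work against deferiprone because it starts from a lowered LIC. The planned end-of-study contrast does not support a direction. Assume a 25% yearly fall from 15 (neither figure is in the documents). The deferoxamine change over 52 weeks is 15 × 0.25 = 3.75. The deferiprone change over 104 weeks from 11.25 is 11.25 × (1 - 0.75²) = 4.92, which is larger.

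**Conclusion.** The point holds in limited form. The contrast in SAP 6.1.2 and 6.3.3 cannot by itself show that deferiprone maintained or further improved iron control, and with a fixed order it cannot separate drug from period. This needs no numerical assumption.

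If the shells are followed on their natural reading, the type I error at a nominal two-sided 5% is about 11% at r = -0.5, correct at r = 0 and about 2% at r = +0.3. The direction of the error is unknown. These figures assume equal SDs for the two changes; unequal SDs bring the SE ratio closer to 1 for a given r.

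The consequence is modest. This is a supplementary efficacy analysis in a study whose primary objective is safety, and no decision rule depends on it. It is still worth correcting before the analysis is run.

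**What to change.** - **SAP 6.1.2 and 6.3.3:** assign the switch purpose to the within-patient change from Week 0 in Group 2 that is already planned, refer to shells 14.2.1.3 and 14.2.2.3, and add a 95% CI. A non-significant test alone does not show that control was maintained; the interval shows how much worsening remains compatible with the data.
- **Deferoxamine-versus-deferiprone contrast:** keep it as supportive only, in switched patients with scans in both periods, using a paired t-test and stating that order and drug cannot be separated. Expressing each change as a percentage of its starting value is optional.
- **Shells 14.2.1.4 and 14.2.2.4:** relabel the test as paired, show one common N, and reword the footnote to say that both columns are the same switched patients.

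Pairing does not resolve the unequal periods (52 weeks on deferoxamine, up to 104 on deferiprone); that is a separate matter.

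The cost is SAP wording and shell edits, with no new data. The downside is that any deferoxamine patients who did not switch leave the table.

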6.2 Study Populations

Study populations intended for analysis are defined as follows: Intent-to-Treat (ITT), Per-Protocol (PP), and Safety. The ITT population will represent the primary analysis population

to evaluate all efficacy endpoints. The efficacy endpoints will also be analyzed for the PP population, which is the secondary analysis population.

6.2.1 Intent-to-Treat Population

The ITT population will include all randomized patients who received at least one dose of study drug and have a baseline and at least one post-baseline efficacy assessment.

6.2.2 Per Protocol Population

The Per-Protocol (PP) population will include all enrolled patients who complete the study, have no major protocol violations, and have an efficacy assessment at the end of the study. Prior to database lock, patients with major protocol violations will be reviewed and excluded, where appropriate, from the PP population. Major protocol violations will include (but not be limited to) the following:

- Patients who were not compliant with the treatment (<80% compliance)
- Patients who took iron chelator medications other than the assigned study medication during the course of the study

6.2.3 Safety Population

The safety population will include all enrolled patients who took at least one dose of study drug.

6.3 Data Analysis

6.3.1 Patient Disposition and Drug Exposure

Patient disposition will be summarized and presented, including the number and percentages of patients who were enrolled, received at least one dose of study medication, completed the study, and withdrew (including reasons for withdrawals). For each patient, the number of doses taken will be computed from the study drug dispensing and accountability eCRFs obtained at each visit. The overall mean of total daily dose taken during the study will be summarized with descriptive statistics.

6.3.2 Patient Characteristics

Baseline characteristics for continuous variables will be summarized with descriptive statistics such as mean, standard deviation, minimum, median and maximum values. Baseline characteristics for discrete variables will be summarized with frequency tables.

6.3.3 Analysis of Efficacy

Changes in LIC, in cardiac MRI T2*, and in serum ferritin from baseline to Year 1 (both groups; Group 1 data are from LA38-0411), from baseline to Year 2 (both groups), and from

baseline to Year 3 (Group 1 only) will be summarized with descriptive statistics and will be tested against no change using a one-sample t-test. The changes in these 3 efficacy measures from the start of deferiprone therapy to the last visit of LA38-EXT in all patients, irrespective of whether deferiprone therapy was initiated in LA38-0411 or in LA38-EXT, will also be tested using a one-sample t-test. In addition, the percentages of responders will be tabulated for Year 1 (both groups; Group 1 data are from LA38-0411), for Year 2 (both groups), and for Year 3 (Group 1 only) of deferiprone therapy. The change from baseline to end of LA38-041 for deferoxamine and the change from baseline to end of LA38-EXT for deferiprone in Group 2 will be compared.

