4.3 Exclusion Criteria

Patients will be excluded from enrollment in study LA38-EXT if they meet **any** of the following criteria:

- 1. Plan to participate in another clinical trial at any time from the day of enrollment until 30 days post-treatment in the current study
- 2. For only those patients who were treated with deferoxamine in study LA38-0411 (Group 2): Presence of any medical condition (including clinically significant laboratory abnormalities, such as ALT ≥ 5 x ULN or creatinine ≥ 2 x ULN), psychological condition, or psychiatric condition which in the opinion of the investigator would cause participation in the study to be unwise.

- 3. Pregnant, breastfeeding, or planning to become pregnant during the study period.
- 4. Treatment failure after 1 year on deferiprone which in the investigator's judgment indicates the need for the patient to be started on a different iron chelator

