	Visit	N Mean \pm SD (Min, Max)	N Mean \pm SD (Min, Max)	P-value (T-test)
Cardiac MRI T2* (ms)	Baseline	XXX XX.X \pm XX.X (xx.x, xx.x)	XXX XX.X \pm XX.X (xx.x, xx.x)	0xxxx
	Month 6	XXX XX.X \pm XX.X (xx.x, xx.x)	XXX XX.X \pm XX.X (xx.x, xx.x)	0xxxx
	Year 1	XXX XX.X \pm XX.X (xx.x, xx.x)	XXX XX.X \pm XX.X (xx.x, xx.x)	0xxxx
	Year 2	XXX XX.X \pm XX.X (xx.x, xx.x)	XXX XX.X \pm XX.X (xx.x, xx.x)	0xxxx
	Year 3	XXX XX.X \pm XX.X (xx.x, xx.x)	XXX XX.X \pm XX.X (xx.x, xx.x)	0xxxx

Data source: 16.2.11 Listing of cardiac MRI T2*

Table 14.2.2.2 Change in cardiac MRI T2* at each follow-up assessment

		Treatment		
		DFP+DFP	DFO+DFP	
	Visit	N Mean \pm SD (Min, Max)	N Mean \pm SD (Min, Max)	P-value (T-test)
Change in cardiac MRI T2* (ms)	Month 6	XXX xx.x \pm xx.x (xx.x, xx.x)	XXX xx.x \pm xx.x (xx.x, xx.x)	0xxxx
	Year 1	XXX xx.x \pm xx.x (xx.x, xx.x)	XXX xx.x \pm xx.x (xx.x, xx.x)	0xxxx
	Year 2	XXX xx.x \pm xx.x (xx.x, xx.x)	XXX xx.x \pm xx.x (xx.x, xx.x)	0xxxx
	Year 3	XXX xx.x \pm xx.x (xx.x, xx.x)	XXX xx.x \pm xx.x (xx.x, xx.x)	0xxxx

Data source: 16.2.11 Listing of cardiac MRI T2*

Table 14.2.2.3 Change in cardiac MRI T2* for DFO+DFP group – Data from the extension study

		DFO+DFP	
	Visit	N Mean \pm SD (Min, Max)	P-value (One sample T-test)
Change in cardiac MRI T2* (ms)	From Year 1 to Year 2	XXX xx.x \pm xx.x (xx.x, xx.x)	0xxxx
	From Year 1 to Year 3	XXX xx.x \pm xx.x (xx.x, xx.x)	0xxxx

Data source: 16.2.11 Listing of cardiac MRI T2*

Table 14.2.2.4 Change in cardiac MRI T2* for DFO and DFO+DFP groups

		Treatment		
		DFO*	DFO+DFP*	
	Visit	N Mean ± SD (Min, Max)	N Mean ± SD (Min, Max)	P-value (T-test)
Change in cardiac MRI T2* (ms)	End of Study	xxx xx.x ± xx.x (xx.x, xx.x)	Xxx xx.x ± xx.x (xx.x, xx.x)	0.xxxx

Data source: 16.2.11 Listing of cardiac MRI T2*

Note: *Patients in DFO come from LA38-0411 and patients in DFO+DFP comes from LA38-EXT.

Table 14.2.2.5 Responder analysis in cardiac MRI T2* defined as $\geq 20\%$ increase in cardiac MRI T2* from baseline.

	Treatment				P-value (Fisher's exact test)
	DFP+DFP		DFO+DFP		
	N	n (%)	N	n (%)	0.xxxx
Year 1	xxx	xx (xx%)	xxx	xx (xx%)	0.xxxx
Year 2	xxx	xx (xx%)	xxx	xx (xx%)	0.xxxx
Year 3	xxx	xx (xx%)	xxx	xx (xx%)	0.xxxx

Data source: 16.2.11 Listing of cardiac MRI T2*

Table 14.2.2.6 Responder analysis in cardiac MRI T2* defined as $\geq 20\%$ increase in cardiac MRI T2* from baseline for DFO+DFP group – Data from the extension study.

	Treatment	
	DFO+DFP	
	N	n (%)
Year 1	xxx	xx (xx%)
Year 2	xxx	xx (xx%)

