Data source: 16.2.11 Listing of cardiac MRI T2*

Table 14.2.3.1 Serum ferritin each assessment

		Treatment		
		DFP+DFP	DFO+DFP	
	Visit	N Mean \pm SD (Min, Max)	N Mean \pm SD (Min, Max)	P-value (T-test)
Serum Ferritin (μ g/L)	Baseline	XXX, XX.X \pm XX.X (XX.X, XX.X)	XXX XX.X \pm XX.X (XX.X, XX.X)	0xxxx
	Month 3	XXX XX.X \pm XX.X (XX.X, XX.X)	XXX XX.X \pm XX.X (XX.X, XX.X)	0xxxx
	Month 6	XXX XX.X \pm XX.X (XX.X, XX.X)	XXX XX.X \pm XX.X (XX.X, XX.X)	0xxxx
	Month 9	XXX XX.X \pm XX.X (XX.X, XX.X)	XXX XX.X \pm XX.X (XX.X, XX.X)	0xxxx
	Month 12	XXX XX.X \pm XX.X (XX.X, XX.X)	XXX XX.X \pm XX.X (XX.X, XX.X)	0xxxx
	Month 15	XXX XX.X \pm XX.X (XX.X, XX.X)	XXX XX.X \pm XX.X (XX.X, XX.X)	0xxxx
	Month 18	XXX XX.X \pm XX.X (XX.X, XX.X)	XXX XX.X \pm XX.X (XX.X, XX.X)	0xxxx
	Month 21	XXX XX.X \pm XX.X (XX.X, XX.X)	XXX XX.X \pm XX.X (XX.X, XX.X)	0xxxx
	Month 24	XXX XX.X \pm XX.X (XX.X, XX.X)	XXX XX.X \pm XX.X (XX.X, XX.X)	0xxxx
	Month 27	XXX XX.X \pm XX.X (XX.X, XX.X)	XXX XX.X \pm XX.X (XX.X, XX.X)	0xxxx
	Month 30	XXX XX.X \pm XX.X (XX.X, XX.X)	XXX XX.X \pm XX.X (XX.X, XX.X)	0xxxx
	Month 33	XXX XX.X \pm XX.X (XX.X, XX.X)	XXX XX.X \pm XX.X (XX.X, XX.X)	0xxxx

		Treatment		
		DFP+DFP	DFO+DFP	
	Month 36	XXX xx.x ± xx.x (xx.x, xx.x)	XXX xx.x ± xx.x (xx.x, xx.x)	0xxxx

Data source: 16.2.16 Listing of serum ferritin

Table 14.2.3.2 Change in serum ferritin at each follow-up assessment

		Treatment		
		DFP+DFP	DFO+DFP	
	Visit	N Mean ± SD (Min, Max)	N Mean ± SD (Min, Max)	P-value (T-test)
Change in serum ferritin (µg/L)	Month 3	XXX xx.x ± xx.x (xx.x, xx.x)	XXX xx.x ± xx.x (xx.x, xx.x)	0xxxx
	Month 6	XXX xx.x ± xx.x (xx.x, xx.x)	XXX xx.x ± xx.x (xx.x, xx.x)	0xxxx
	Month 9	XXX xx.x ± xx.x (xx.x, xx.x)	XXX xx.x ± xx.x (xx.x, xx.x)	0xxxx
	Month 12	XXX xx.x ± xx.x (xx.x, xx.x)	XXX xx.x ± xx.x (xx.x, xx.x)	0xxxx
	Month 15	XXX xx.x ± xx.x (xx.x, xx.x)	XXX xx.x ± xx.x (xx.x, xx.x)	0xxxx
	Month 18	XXX xx.x ± xx.x (xx.x, xx.x)	XXX xx.x ± xx.x (xx.x, xx.x)	0xxxx
	Month 21	XXX xx.x ± xx.x (xx.x, xx.x)	XXX xx.x ± xx.x (xx.x, xx.x)	0xxxx
	Month 24	XXX xx.x ± xx.x (xx.x, xx.x)	XXX xx.x ± xx.x (xx.x, xx.x)	0xxxx

		Treatment		
		DFP+DFP	DFO+DFP	
	Month 27	XXX XX.X ± XX.X (xx.x, xx.x)	XXX XX.X ± XX.X (xx.x, xx.x)	0xxxx
	Month 30	XXX XX.X ± XX.X (xx.x, xx.x)	XXX XX.X ± XX.X (xx.x, xx.x)	0xxxx
	Month 33	XXX XX.X ± XX.X (xx.x, xx.x)	XXX XX.X ± XX.X (xx.x, xx.x)	0xxxx
	Month 36	XXX XX.X ± XX.X (xx.x, xx.x)	XXX XX.X ± XX.X (xx.x, xx.x)	0xxxx

Data source: 16.2.16 Listing of serum ferritin

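### SAP 6.3.3 and the efficacy table shells disagree: 12 of 18 planned one-sample tests have no shell, and the shells show 52 Group 1 versus Group 2 p-values that 6.3.3 does not describe

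*SAP*

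**What the plan says.** **Methods text.** SAP 6.3.3 takes the changes in LIC, cardiac MRI T2* and serum ferritin at Year 1 and Year 2 (both groups) and Year 3 (Group 1 only). It states that they "will be summarized with descriptive statistics and will be tested against no change using a one-sample t-test". A further one-sample test covers the change "from the start of deferiprone therapy to the last visit of LA38-EXT in all patients". For responders, it says only that "the percentages of responders will be tabulated for Year 1" and the later years; it names no test. The one comparison it names is within Group 2, deferoxamine period against deferiprone period. Protocol 9.4.1.3 plans the same one-sample tests.

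**Baseline.** SAP 6.1.2 sets Group 1's baseline at the parent-study baseline and Group 2's at extension Week 0. It states that Group 2 has no third year of deferiprone.

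**Shells (SAP 17).** "Table 14.2.1.2 Change in LIC at each follow-up assessment", "Table 14.2.2.2 Change in cardiac MRI T2* at each follow-up assessment" and "Table 14.2.3.2 Change in serum ferritin at each follow-up assessment" each set a DFP+DFP column beside a DFO+DFP column, with a single p-value per row labelled as a t-test. The level tables (14.2.1.1, 14.2.2.1, 14.2.3.1) have the same layout. The responder tables (14.2.1.5, 14.2.2.5, 14.2.3.4) carry a Fisher's exact p-value per year. A one-sample label appears only in Tables 14.2.1.3, 14.2.2.3 and 14.2.3.3, all for DFO+DFP alone.

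**The concern.** The text asks whether iron measures changed from the start of deferiprone. The main shells ask whether two groups differ, and for Group 2 they measure from a different baseline. A programmer who follows the shells as drawn would test a different hypothesis from the one in the methods section.

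The gap falls on Group 1 and on the all-patient analysis. Group 1 is the only group that reaches Year 3 of deferiprone, and the secondary objective concerns treatment for up to 3 years. With 300 patients planned and 2:1 randomization in the parent study, Group 1 would be about 200 of 300, if completion and enrolment are similar in both arms.

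Meanwhile, p-values between the two groups would appear in the report of a study described as single-arm, where a reader could take them for a treatment comparison. If text and shells are not reconciled before lock, the choice between two analyses is left open until data are available.

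**Working it through.** The documents give no test count, alpha or power for this study, so there is no stated figure to reproduce. The check is a count of the tests in SAP 6.3.3 against the rows of the shells in SAP 17.

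**1. Planned one-sample tests (6.3.3), one per group and time point**

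- Yearly changes: 3 measures × (3 Group 1 years + 2 Group 2 years) = 15
- All patients, start of deferiprone to last visit: 3 measures × 1 = 3
- Total: 15 + 3 = 18

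**2. Planned tests that have a shell**

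- Tables 14.2.1.3 and 14.2.2.3: Year 1 to Year 2 and Year 1 to Year 3, so 2 + 2 = 4
- Table 14.2.3.3: Month 12 to 24 and Month 12 to 36 match the plan, so 2. Its other 6 rows go beyond 6.3.3.
- Covered: 4 + 2 = 6. Not covered: 18 − 6 = 12, namely Group 1 (3 × 3 = 9) and all patients (3).

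If *both groups* in 6.3.3 means the two groups pooled, the plan has 3 × 3 + 3 = 12 tests, and none of them matches a shell.

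**3. Group 1 versus Group 2 p-values in the shells**

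| Measure | Level rows | Change rows | Responder rows | Total | At or before Month 12 | After Month 12 |
|---|---|---|---|---|---|---|
| LIC | 5 | 4 | 3 | 12 | 6 | 6 |
| Cardiac MRI T2* | 5 | 4 | 3 | 12 | 6 | 6 |
| Serum ferritin | 13 | 12 | 3 | 28 | 10 | 18 |
| All | 23 | 20 | 9 | 52 | 22 | 30 |

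The count leaves out the planned within-Group 2 comparison (14.2.1.4, 14.2.2.4) and the baseline table (14.1.6).

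**4. Which clock the shells use**

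The two-group shells give DFO+DFP a Year 3 or Month 36 row with a p-value, and the Group 2 ferritin table starts from Month 12. Both fit time since parent-study baseline, with Month 12 as extension Week 0. They do not fit 6.1.2. The labels also clash between neighbouring tables: Year 1 is the starting point in 14.2.1.3 but a follow-up time in 14.2.1.6, and both are headed as extension data.

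- On the parent-study clock, 22 rows are at or before Month 12. Three of these are baseline rows; the rest compare concurrent deferiprone and deferoxamine. In the other 30 rows Group 1 has had a year more of deferiprone than Group 2.
- On the 6.1.2 clock, Group 2 cannot fill rows beyond Month 24 (LIC 3 + T2* 3 + ferritin 9 = 15). Nor can it fill the Month 6 MRI rows (2 + 2 = 4), because extension MRI is at Visits 1, 5 and 9 only. That is 19 rows, leaving 52 − 19 = 33.

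**5. What can still be recovered**

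The change shells print N, mean and SD for Group 1, so t = mean / (SD / √N) gives its nine tests, apart from rounding. The efficacy table shells have no all-patient column, so the three all-patient tests cannot be obtained this way.

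**The case against.** **The shells are part of the SAP and are not final.** The protocol synopsis allows additional analyses with details in the SAP, and Protocol 9.4 has the SAP approved before database lock. SAP 17 says that the tables may differ from the shells, and SAP 14 foresees added tables. Nothing says that the shells override 6.3.3. This stands. The 52 p-values are undescribed in the methods text, but they are not outside the SAP, and a missing shell is not a missing result. However, SAP 17 also says that the shells reflect the general layout of the report, and a change of hypothesis and baseline is more than layout.

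**Many of the contrasts are between randomized arms.** This also stands in part. On the shells' clock, 22 of the 52 are baseline or concurrent comparisons of arms randomized 2:1 in the parent study, weakened by selection into the extension.

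**Selection into the extension.** A reader might infer that the entry criteria inflate the false-positive rate of the between-group tests by a calculable amount. Exclusion 2 in Protocol 4.3 applies to Group 2 only. Exclusion 4, "Treatment failure after 1 year on deferiprone", can remove only Group 1 patients. The filters do differ, but the documents give no removal rate. Exclusion 4 rests on the investigator's judgment, not on a measured change. It is also unsettled whether excluded patients leave the Year 1 analysis: the ITT definition refers to all randomized patients, and Group 1's Year 1 data come from the parent study. No size can be put on this.

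**Efficacy is secondary.** The primary objective is safety, and no confirmatory efficacy claim is stated. This limits the weight of the point.

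**Conclusion.** The inconsistency is real. Per group and per analysis population, 12 of the 18 one-sample tests in 6.3.3 have no shell: 9 for Group 1 and 3 for all patients. The shells show 52 Group 1 versus Group 2 p-values that 6.3.3 does not describe, on a clock that contradicts the Group 2 baseline in 6.1.2. Of these, 30 fall after Month 12, with unequal deferiprone exposure.

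The counts assume a separate test for each group, and they double if the tables are repeated for the per-protocol population. The pooled reading also leaves 12 tests without a shell.

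Two stronger readings are not supported. One is that the secondary objective will go untested in Group 1: that requires the methods text to be ignored, and the nine Group 1 statistics follow from the printed summaries in any case. The other is that all 52 contrasts are non-comparable, which does not fit the 22 at or before Month 12.

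This should be fixed before database lock. It goes beyond missing detail, because text and shells test different hypotheses, but it concerns a secondary objective and can be repaired within the SAP.

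**What to change.** Before database lock:

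1. For each measure, add a one-sample table for Group 1 at Years 1, 2 and 3 (N, mean change, 95% CI, p-value), and one for all patients from start of deferiprone to the last LA38-EXT visit.
2. Keep the Group 2 one-sample tests in Tables 14.2.1.3, 14.2.2.3 and 14.2.3.3, relabelled as baseline (extension Week 0) to Year 1 and to Year 2 of deferiprone.
3. Put the two-group change and responder shells on the 6.1.2 clock, with no Group 2 Year 3 row and no Group 2 Month 6 MRI row.
4. Remove the Group 1 versus Group 2 p-values from the level tables (14.2.1.1, 14.2.2.1, 14.2.3.1), the change tables (14.2.1.2, 14.2.2.2, 14.2.3.2) and the responder tables (14.2.1.5, 14.2.2.5, 14.2.3.4). If any are kept, describe them in 6.3.3 as exploratory.

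The missing tests should have their own tables. Adding per-group one-sample p-values to the present change shells would give (4 + 4 + 12) × 2 = 40 p-values against 15 planned yearly tests. It would duplicate the Group 2 tables, and on the current clock the Group 2 Year 1 row would test a deferoxamine change.

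The cost is minor shell and programming work, with no effect on patients or data collection. The report loses between-group p-values that no stated objective calls for.
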